3.3.1.3 Supplementary analysis

Secondary estimands of key secondary efficacy endpoints 2a and 2b

Under hypothetical strategy, measurements after treatment discontinuation and/or initiation of rescue medication will be considered as missing data.

A MMRM, under the missing at random framework, will be performed for the secondary estimands of both key secondary efficacy endpoints 2a and 2b. The model will include treatment, randomization stratum of HbA1c, randomization stratum of previous OADs, visit, treatment-by-visit interaction as fixed effects, appropriate baseline value and baseline-by-visit interaction as continuous covariate. For the analysis of HbA1c, the randomization stratum of HbA1c will be removed from the MMRM model given that the baseline HbA1c continuous value is already in the model. The MMRM model will be implemented using SAS® (Version 9.4 or higher) MIXED procedure (PROC MIXED) with an unstructured correlation matrix to model the within-participant errors. Parameters will be estimated using the restricted maximum likelihood method with the Newton-Raphson algorithm. Denominator degree of freedom will be estimated using the Kenward-Roger approximation by fitting values from post-randomization scheduled visits. LS Means difference between treatments, SE, 2-sided 97.5% CI, and 2-sided superiority p-value from MMRM will be provided if endpoint is to be tested as per the gate-keeping procedure defined in [Section 3.5](#); otherwise, 95% CI will be provided and no p-value will be provided.

3.3.2 Other secondary endpoints

3.3.2.1 *Definition of endpoints*

The other secondary endpoints are:

- Change in fasting plasma glucose from baseline to Week 24
- Change in 7-point self-monitored plasma glucose (SMPG) profile from baseline to Week 24 (each time point and average daily value)
- Proportion of participants reaching HbA1c target <7% at Week 24 with no hypoglycemia (defined as ADA level 1, 2 or 3) during treatment
- Proportions of participants reaching HbA1c target <7% at Week 24 with no clinically relevant hypoglycemia (defined as ADA level 2 or 3) during treatment
- Total insulin dose in each group at Week 24, defined as the sum of the insulin dose in U and U/kg from IMP and NIMP (eg, rescue therapy).
- Percentage of participants requiring rescue therapy during the 24-week treatment period
- Change in fasting C-peptide from baseline to Week 24

3.3.2.2 *Main analytical approach*

The other secondary endpoints of will be analyzed with the primary estimand defined according to the following attributes:

- Treatment condition: iGlarLixi will be compared to IDegAsp.
- Analysis population: All randomized participants for all endpoints, and additionally safety population for total insulin dose.
- Intercurrent events (IE):

- For total insulin dose in each group at Week 24
 - Treatment discontinuation IE will be handled with the hypothetical strategy: the endpoint will be considered as missing after treatment discontinuation
 - The initiation of rescue medication IE will be handled with the treatment policy strategy: the endpoint will be assessed based on all assessments irrespective of the initiation of rescue medication
- For percentage of participants requiring rescue therapy during the 24-week treatment period
 - Treatment discontinuation IE will be handled with the treatment policy strategy: the endpoint will be assessed based on all assessments irrespective of the treatment discontinuation
- For other endpoints:
 - Both treatment discontinuation IE and initiation of rescue medication IE will be handled with the treatment policy strategy: the endpoint will be assessed based on all assessments irrespective of the IE
- Population-level summary:
 - For change in FPG, 7-point SMPG and fasting C-peptide from baseline to Week 24: LS Means difference between treatments from ANCOVA with the same analysis approach as of the primary estimand of the primary endpoint, except that the baseline of each endpoint will be included in the model rather than baseline HbA1c. Descriptive statistics for results and changes from baseline will be provided for baseline and each visit by treatment group. Mean changes from baseline with the corresponding standard error will be plotted over time. For 7-point SMPG, the average and each time point will be analyzed.
 - For total insulin dose in each group at week 24: LS mean difference between treatments, as well as SE and 2-sided 95% CI, from MMRM with treatment, randomization stratum of HbA1c, randomization stratum of previous OADs, visits and treatment-by-visit interaction as fixed effects. Descriptive statistics for percentage change from starting dose will be provided. Raw data and changes from starting dose with the corresponding standard error will be plotted over time.
 - For binary endpoints: Odds ratio between treatments from logistic regression model adjusting for treatment group, randomization stratum of previous OADs, baseline continuous HbA1c and appropriate baseline covariates. The proportion of participants in each treatment group will be provided, as well as the odds ratio between groups with associated 2-sided 95% CI. For the categorical secondary endpoints in which HbA1c is assessed at Week 24, all values at Week 24 will be used to determine whether a participant is a responder or not, even if they are measured after IMP discontinuation or introduction of rescue therapy. If no assessment is available at Week 24, participants will be treated as non-responders.

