9.3.3.2 Other secondary endpoints

See [Section 3](#) for other secondary efficacy endpoints. Unless otherwise specified, other secondary endpoints will be analyzed in the treatment policy framework using the ITT population.

| Population | Strategy for accounting for intercurrent events | Endpoint | Population level summary |
|-----------------------------|--|--|---------------------------------------|
| All randomized participants | Treatment policy strategy for both intercurrent events: 
 • Treatment discontinuation • Initiation of rescue medication | Change from baseline to Week 24 in: 
 • FPG • 7-point SMPG • Fasting C-peptide | LS mean difference between treatments |
| | | If a participant at Week 24 achieves: 
 • HbA1c < 7% and no hypoglycemia (any hypoglycemia ADA level 1, 2 or 3) • HbA1c < 7% and no clinically relevant hypoglycemia (any hypoglycemia ADA level 2 or 3) • Initiation of rescue medication | Odds ratio between treatments |

Descriptive statistics (Number, mean, SD, median, minimum, and maximum) will be provided by treatment for FPG, 7-point SMPG and fasting C-peptide at the scheduled visits. Descriptive statistics (Number, mean, SD, median, minimum, and maximum) will be provided by treatment for total insulin dose.

For continuous secondary endpoints, such as change from baseline in FPG, 7-point SMPG and fasting C-peptide, they will be analyzed using the same approach as the primary endpoint to compare iGlarLixi with IDegAsp. The model will include treatment group, randomization strata of HbA1c and the corresponding baseline for that endpoint. Details will be provided in the SAP.

Other secondary categorical efficacy endpoints defined in [Section 3](#) will be analyzed using a logistic regression model same with the key secondary categorical endpoints. Details of the logistic model will be discussed in the SAP.

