1.1 STUDY DESIGN

- Open-label, 1:1 randomized, active-controlled, 2 treatment-arm, 24-week treatment duration, parallel-group, multicenter phase 3 study
- Participants with type 2 diabetes mellitus (T2DM) treated with metformin ± one additional oral antidiabetic drug (OAD) would be recruited in this study.
- The randomization will be stratified by value of screening HbA1c (<8%, ≥8%), and by use at screening of metformin alone or metformin + SGLT-2i (Yes/No), ie, by oral antidiabetic treatment use at screening (metformin ± SGLT-2i / metformin + OAD other than SGLT-2i). The overall objective of this last stratification group is to ensure that participants who will need to discontinue their second OAD are well balanced between groups
- Total duration of study participation for each participant is up to 27 weeks.
- This study comprises of 3 periods:
 - An up-to 2-week screening period during which: a sulfonylurea (SU), a glinide, an alpha-glucosidase inhibitor (alpha-GI), or a dipeptidyl-peptidase-4 (DPP-4) inhibitor, if previously taken, will be discontinued. Sodium-glucose co-transporter 2 (SGLT-2) inhibitor, if previously taken, will be kept at the stable dose; metformin treatment will maintain at the stable dose (at least 1000 mg/day or a maximal tolerated dose).
 - A 24-week, open-label randomized treatment period with iGlarLixi or IDegAsp, both on top of metformin ± SGLT-2 inhibitor.
 - A 3-day post-treatment safety follow-up period.
- Screening is from signed informed consent to randomization.

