3.2.2 Main analytical approach

The null and the alternative hypotheses based on non-inferiority margin of 0.3% are described as:

$$H_0: i\text{GlarLixi} - \text{IDegAsp} \geq 0.3\% \text{ versus } H_a: i\text{GlarLixi} - \text{IDegAsp} < 0.3\%$$

If the upper bound of the two-sided 95% confidence interval for the difference of iGlarLixi – IDegAsp is smaller than 0.3%, the study will be considered to have met its primary objective and the non-inferiority of iGlarLixi over IDegAsp is established.

The primary endpoint will be analyzed with the primary estimand defined according to the following attributes:

- Endpoint: Change in HbA1c from baseline to Week 24.
- Treatment condition: iGlarLixi will be compared to IDegAsp.
- Analysis population: All randomized participants
- Intercurrent events (IE):
 - Treatment discontinuation IE will be handled with the treatment policy strategy: the endpoint will be assessed based on all assessments irrespective of the treatment discontinuation
 - The initiation of rescue medication IE will be handled with the treatment policy strategy: the endpoint will be assessed based on all assessments irrespective of the initiation of rescue medication
- Population-level summary: LS Means difference between treatments from analysis of covariance (ANCOVA) with treatment groups and previous OADs as fixed effects, and baseline HbA1c continuous value as covariate. Standard errors (SE), 2-sided 95% confidence intervals (CI) and 2-sided non-inferiority p-value from ANCOVA will be provided. Missing data will be imputed by multiple imputations using missingness patterns based on treatment completion, and under the missing at random (MAR) assumption within each pattern.
 - For participants completing the 24-week treatment period, the missing HbA1c values will be imputed using data from other participants completing the treatment.

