 - For participants discontinuing prematurely the treatment, the missing HbA1c values will be imputed using data from participants also discontinuing treatment but having their HbA1c assessment (retrieved dropouts). In case there are not enough observed Week 24 data post treatment discontinuation, ie, less than 10 in either arm, or the model does not converge, whichever happens, return-to-baseline (RTB) approach will be used for imputation; missing HbA1c values at Week 24 will be imputed from a normal distribution with the expected value set to the participant's baseline value and standard deviation based on the baseline value by treatment group.

Missing HbA1c values will be imputed 1000 times to generate 1000 datasets with complete HbA1c values using SAS procedure for multiple imputation (PROC MI). The imputation model will include the treatment group as fixed effect, and baseline, Week 8, Week 12 and Week 18 HbA1c continuous value as covariate. The randomization stratum of HbA1c can be removed from the model given that the baseline HbA1c continuous value is already in the model.

For each of the 1000 imputed datasets, the change in HbA1c from baseline to Week 24 will be analyzed using an ANCOVA with treatment groups and previous OADs as fixed effects, and baseline HbA1c continuous value as covariate. The results obtained from analyzing the datasets will be combined using Rubin's rule to draw inference.

The non-inferiority will be assessed using the upper bound of the 2-sided 95% confidence interval (CI). If the upper bound of the 95% CI is less than 0.3%, the non-inferiority of iGlarLixi versus IDegAsp will be claimed.

Descriptive statistics for HbA1c results and changes from baseline will be provided for baseline and each visit by treatment group. Mean changes from baseline with the corresponding standard error will be plotted over time.

Missing data assumption check

The following analyses will be performed on the ITT population to explore the missing data frequency and pattern in the primary efficacy analysis:

- To explore missing data patterns for HbA1c in the primary efficacy analysis, number (%) of participants and number (%) of participants by baseline characteristics will be presented by the following missing data pattern and by treatment group. Descriptive statistics and plots for HbA1c results and changes from baseline will be provided by missing data pattern and by treatment group:

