3.3.1 Key secondary efficacy endpoints

3.3.1.1 *Definition of endpoints*

The key secondary efficacy endpoints are:

- 2a The absolute change from baseline to week 24 in HbA1c.
- 2b The absolute change from baseline to week 24 in body weight.
- 2c Proportion of participants reaching HbA1c<7% at week 24.
- 2d Proportion of participants reaching HbA1c targets <7% without body weight gain at Week 24.
- 2e Proportion of participants reaching HbA1c <7% with no body weight gain at Week 24 and no hypoglycemia (defined as ADA level 1, 2 or 3) during treatment.

3.3.1.2 *Main analytical approach*

Key secondary efficacy endpoint 2a

If the primary objective is met, the key secondary efficacy endpoint 2a will be analyzed with the primary estimand defined the same as the primary estimand of the primary endpoint, except that 2-sided 97.5% CI and superiority p-value from ANCOVA will be provided if endpoint is to be tested as per the gate-keeping procedure defined in [Section 3.5](#); otherwise, 95% CI will be provided and no p-value will be provided.

Key secondary efficacy endpoint 2b

The key secondary efficacy endpoint 2b will be analyzed with the primary estimand defined according to the following attributes

- Endpoint: Change in body weight from baseline to Week 24.
- Treatment condition: iGlarLixi will be compared to IDegAsp.
- Analysis population: All randomized participants
- Intercurrent events (IE):
 - Treatment discontinuation IE will be handled with the treatment policy strategy: the endpoint will be assessed based on all assessments irrespective of the treatment discontinuation
 - The initiation of rescue medication IE will be handled with the treatment policy strategy: the endpoint will be assessed based on all assessments irrespective of the treatment discontinuation
- Population-level summary: LS Means difference between treatments from ANCOVA with treatment group, randomization stratum of HbA1c and previous OAD and baseline body weight as covariates. SE, 2-sided 97.5% CI and superiority p-value from ANCOVA will be provided if endpoint is to be tested as per the gate-keeping procedure defined in

[Section 3.5](#); otherwise, 95% CI will be provided and no p-value will be provided. Missing data will be imputed by multiple imputations using missingness patterns based on treatment completion, and under the missing at random (MAR) assumption within each pattern. The same imputation method as of the primary estimand of the primary endpoint will be used.

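### Read literally, the SAP's ANCOVA for FPG, 7-point SMPG and fasting C-peptide has no HbA1c term, although screening HbA1c is a randomization stratum and the protocol adjusts for it

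*SAP*

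**What the plan says.** SAP 1.1 states: "The randomization will be stratified by value of screening HbA1c" (below 8%, or 8% and above). The second factor is oral antidiabetic use at screening.

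The primary analysis in SAP 3.2.2 is an "analysis of covariance (ANCOVA) with treatment groups and previous OADs as fixed effects, and baseline HbA1c continuous value as covariate". SAP 3.3.2.2 applies the same approach to FPG, 7-point SMPG and fasting C-peptide, "except that the baseline of each endpoint will be included in the model rather than baseline HbA1c".

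SAP 3.2.2 also says: "The randomization stratum of HbA1c can be removed from the model given that the baseline HbA1c continuous value is already in the model". That sentence concerns the imputation model for the primary endpoint. SAP 3.2.3 and 3.2.4 give the same reason for the HbA1c MMRMs, and so does 3.3.1.3: "For the analysis of HbA1c, the randomization stratum of HbA1c will be removed from the MMRM model".

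Where a continuous endpoint is modelled without baseline HbA1c, the SAP otherwise keeps the stratum:
- body weight ANCOVA (3.3.1.2): "with treatment group, randomization stratum of HbA1c and previous OAD and baseline body weight as covariates";
- body weight MMRM (3.3.1.3), where the stratum is dropped for HbA1c only;
- total insulin dose MMRM (3.3.2.2): "randomization stratum of HbA1c, randomization stratum of previous OADs, visits and treatment-by-visit interaction as fixed effects".

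The protocol has two statements. Synopsis 1.1 adjusts continuous secondary endpoints for treatment, the randomization strata and suitable baseline covariates. Section 9.3.3.2 says of these three endpoints: "The model will include treatment group, randomization strata of HbA1c and the corresponding baseline for that endpoint". It does not mention previous OADs, and it leaves details to the SAP. SAP section 1 reports no major change from the protocol's analyses.

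**The concern.** An analysis normally reflects the factors used to stratify randomization. Stratifying makes the arms more alike on HbA1c. If HbA1c predicts the outcome and is left out of the model, its variance stays in the residual, and the standard error ignores the balance that the design bought.

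The texts also differ. The synopsis names both strata, Protocol 9.3.3.2 names HbA1c but not previous OADs, and SAP 3.3.2.2 keeps previous OADs but loses HbA1c. An analyst could follow the SAP to the letter, or could put the stratum back because the stated reason for removing it has gone.

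The one clause governs ten treatment comparisons: FPG, fasting C-peptide, seven SMPG time points and the SMPG daily average (1 + 1 + 7 + 1 = 10). What is at stake is a little precision, and a single model fixed before the data are seen.

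**Working it through.** **1. The model, term by term**

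| Source | Treatment | HbA1c | Previous OADs | Own baseline |
|---|---|---|---|---|
| SAP 3.2.2, primary ANCOVA | yes | continuous baseline | yes | (is HbA1c) |
| SAP 3.3.2.2, FPG / SMPG / C-peptide | yes | **none** | yes | yes |
| SAP 3.3.1.2, body weight | yes | stratum | yes | yes |
| SAP 3.3.2.2, insulin dose MMRM | yes | stratum | yes | none listed |
| Protocol synopsis 1.1 | yes | stratum | stratum | suitable covariates |
| Protocol 9.3.3.2, these endpoints | yes | stratum | not named | yes |

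The responder models (3.3.1.2, 3.3.2.2) carry continuous baseline HbA1c, and the hypoglycemia models (3.6.3.2) carry the stratum. These three endpoints are the exception.

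**2. The plan's own figure**

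The documents give no interval width or correlation for these endpoints. The only design figure is the sample size (SAP 4): margin 0.3, SD 1.05, true difference 0, 90% power, two-sided 0.05, 10% dropout.

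n per arm = 2 × (1.05/0.3)² × (1.960 + 1.282)² ≈ 258, or 259 with the t distribution. Dividing by 0.9 gives 287 or 288, against 290 stated. The figure reproduces, so 580 is used below.

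**3. Widening with complete data**

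The comparison is the literal SAP model against the same model plus the HbA1c stratum. Every effect size is assumed.

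Let d be the difference between HbA1c strata in residual SDs, after own baseline and previous OADs, and p the share in one stratum. Ignoring any overlap between the stratum and the other covariates, the ratio of widths is √(1 + p(1−p)d²).

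| d | p = 0.5 | p = 0.8 |
|---|---|---|
| 0 | 1.000 | 1.000 |
| 0.2 | √1.0100 = 1.005 | √1.0064 = 1.003 |
| 0.4 | √1.0400 = 1.020 | √1.0256 = 1.013 |
| 0.6 | √1.0900 = 1.044 | √1.0576 = 1.028 |

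In terms of the stratum's partial correlation r, the ratio is 1/√(1−r²). For r = 0, 0.1, 0.2 and 0.3 it is 1.000, 1.005, 1.021 and 1.048. Actual coverage of a nominal 95% interval, 1 − 2Φ(−1.96 × ratio), is then 95.0%, 95.1%, 95.5% and 96.0%.

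Simulation lets the own baseline overlap with HbA1c. The settings were 580 participants, blocks of 4 within strata, splits of about 50:50, residual SD 1, baseline slope −0.5, an OAD effect of 0.2 SD and no treatment effect. For d = 0, 0.2, 0.4 and 0.6 the ratios were:
- 1.000, 1.005, 1.018 and 1.040 when own baseline correlates 0.4 with the variable behind the HbA1c stratum;
- 1.000, 1.003, 1.014 and 1.030 when it correlates 0.7.

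The average treatment estimate stayed within 0.003 SD of zero (Monte Carlo SE 0.0019).

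**4. Widening under imputation**

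The planned imputation model lacks the stratum, so imputed values carry little of its effect. The setting with correlation 0.4 was repeated with values imputed from treatment and own baseline only (20 imputations, a few hundred runs per setting).

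| d | Complete | 10% missing | 20% missing |
|---|---|---|---|
| 0.4 | 1.8% | 1.3% | 0.9% |
| 0.6 | 4.0% | about 2.8% | about 1.9% |

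No bias was visible. The simulation did not reproduce imputation by treatment completion, the return-to-baseline fallback or intermediate visit values.

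**5. Against Protocol 9.3.3.2 taken alone**

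That model has the HbA1c stratum but no OAD term, so the difference can go either way. Simulated ratios of SAP width to protocol width ran from 0.982 (d = 0, OAD effect 0.4) to 1.038 (d = 0.6, OAD effect 0).

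**The case against.** The model as written is a coherent ANCOVA. Baseline FPG and SMPG are themselves glycemic measures and may carry most of what HbA1c would add, so the comparison with body weight is weaker for them. The insulin dose model is not a close parallel either, since it lists no baseline covariate. The sentence in SAP 3.2.2 on removing the stratum is about imputation and sets no rule for this ANCOVA. The synopsis and the SAP's statement of no major changes make the intended model largely recoverable. On precision alone the gain is small, may be nil, and shrinks under the planned imputation.

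Most of this stands, and it limits the point to a minor one. It does not remove it. The glycemic-baseline argument does not reach C-peptide. The same reason for dropping the stratum is given for analysis models in SAP 3.2.3, 3.2.4 and 3.3.1.3, so it is not confined to imputation. A model that has to be recovered from the protocol is not the one the SAP states.

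A reader might infer something stronger: that the omission biases these comparisons or makes their intervals anti-conservative. Neither follows. Randomization within strata balances HbA1c, and the interval errs on the wide side if at all. A reader might also infer a deliberate departure from the protocol. The documents do not show one; an incomplete cross-reference explains the text equally well.

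**Conclusion.** The gap in the text is clear: read literally, these three endpoints have no HbA1c term, contrary to both protocol statements and to the SAP's own practice elsewhere. The effect is a possible small loss of precision. With assumed stratum effects of 0 to 0.6 residual SD, the interval is about 0% to 4% wider with complete data and about 0% to 3% wider with 10% missing under the simplified imputation. The lower end is more plausible where own baseline already reflects HbA1c. None of these percentages is a document figure, and a stronger stratum effect than assumed would give more.

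No bias is expected. The endpoints lie outside the hierarchical testing procedure in SAP 3.5, so neither the primary nor any key secondary conclusion changes. This is worth correcting, at low priority.

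**What to change.** In SAP 3.3.2.2, write out the ANCOVA for change in FPG, 7-point SMPG and fasting C-peptide as treatment, HbA1c randomization stratum, previous-OAD randomization stratum and the endpoint's own baseline. This matches the body weight model in SAP 3.3.1.2, agrees with the protocol synopsis, and supplies the term missing from each of Protocol 9.3.3.2 and SAP 3.3.2.2.

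The cost is one sentence, data already held from randomization, and one degree of freedom (the t critical value at 580 moves from 1.96409 to 1.96410). Adding the two strata to the imputation model for these endpoints is optional. It would bring the imputation and analysis models into line and keep more of the gain when data are missing.

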5.2 EXCLUSION CRITERIA

Participants are excluded from the study if any of the following criteria apply:

Medical conditions

- E 01. Participant who has a severe renal function impairment with an estimated glomerular filtration rate (eGFR) <30 mL/min/1.73m²
- E 02. Pregnant or breast-feeding woman.
- E 03. Woman of childbearing potential not protected by highly effective contraceptive method of birth control and/or who is unwilling or unable to be tested for pregnancy
- E 04. Conditions/situations such as:
 - Participant with short life expectancy.
 - Participant with conditions/concomitant diseases making him/her not evaluable for the primary efficacy endpoint (eg, hemoglobinopathy or hemolytic anemia, receipt of blood or plasma products within 3 months prior to screening).
 - Participant with conditions/concomitant diseases precluding his/her safe participation in this study (eg, active malignant tumor, major systemic diseases, presence of clinically significant diabetic retinopathy or presence of macular edema likely to require laser treatment within the study period).
 - Uncooperative or any condition that could make the participant potentially non-compliant to the study procedures (eg, participant unable or unwilling to do self-injections or blood glucose monitoring using the Sponsor-provided blood glucometer at home).

Prior/concomitant therapy

- E 05. Previous treatment with insulin (except for short-term treatment ≤ 14 days due to intercurrent illness at the discretion of the Investigator) within 1 year prior to screening.
- E 06. Use of oral or injectable glucose-lowering agents other than those stated in the inclusion criteria within 3 months prior to screening.
- E 07. Use of systemic glucocorticoids (excluding topical application or inhaled forms) for 1 week or more within 3 months prior to screening.
- E 08. Use of weight loss drugs within 3 months prior to screening.
- E 09. History of discontinuation of a previous treatment with GLP-1 RAs due to safety/tolerability reasons or lack of efficacy.
- E 10. Use of any investigational drug other than specified in this protocol within 1 month or 5 half-lives, whichever is longer, prior to screening.

Other exclusions

- E 11. Laboratory findings tested at the screening visit:
 - Amylase and/or lipase >3 times the upper limit of normal (ULN) laboratory range.
 - Alanine aminotransferase (ALT) or aspartate aminotransferase (AST) >3 ULN.

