5.3 APPENDIX 3 DEMOGRAPHICS AND BASELINE CHARACTERISTICS, PRIOR OR CONCOMITANT MEDICATIONS

Demographics, baseline characteristics, medical surgical history

The following demographics and baseline characteristics, medical and surgical history and diabetes history will be summarized using descriptive statistics in the randomized population.

Demographic and baseline characteristics

- age in years as quantitative variable and in categories (<50, \geq 50 to <65, \geq 65 to <75, \geq 75)
- gender (Male, Female)
- race (Asian)
- baseline body mass index (BMI) in kg/m² as quantitative variable and in categories (<24, \geq 24 to 28, \geq 28)
- randomization stratum of screening HbA1c (<8%, \geq 8%)
- randomization stratum of oral antidiabetic use at screening (Metformin \pm SGLT-2i, Metformin + other OAD)

Baseline efficacy characteristics

- HbA1c % as quantitative variable
- body weight in kg as quantitative variable
- fasting plasma glucose in mmol/L as quantitative variable

- 7-point SMPG in mmol/L as quantitative variable in daily average
- fasting C-peptide level in nmol/L as quantitative variable and by quartiles

Baseline safety will be presented along with the safety summaries.

General medical/surgical history will be collected. Medical and surgical history will be coded to a LLT, PT, HLT, HLGT, and associated primary SOC using the MedDRA version currently in effect at Sanofi at the time of database lock.

Diabetes history

- Duration of type 2 diabetes in years derived as: (Date of informed consent – Date of diagnosis of diabetes + 1)/365.25
- Age at onset of diabetes in years derived as: Year of diagnosis of diabetes – Year of birth
- Duration of prior metformin treatment in years derived as: (Date of informed consent - Date of first intake of metformin + 1)/365.25
- Baseline daily dose metformin in mg as quantitative variable and in categories (<1000, \geq 1000 to <1500, \geq 1500 to <2500, \geq 2500)
- Prior use of SGLT-2i (Yes, No)
- Duration of prior SGLT-2i treatment in years derived as: (Date of informed consent – Date of first intake of SGLT-2i + 1)/365.25
- Prior use of OADs other than metformin or SGLT-2i (Yes, No)
- Duration of prior OADs other than metformin or SGLT-2i in years derived as: (Date of informed consent - Date of first intake of OAD + 1)/365.25
- Gestational diabetes
- Diabetic retinopathy
- Diabetic neuropathy
- Diabetic nephropathy

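### The total insulin dose MMRM adjusts only for the two dichotomous randomization strata and uses no continuous baseline covariate, although baseline body weight and HbA1c are collected.

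*SAP*

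**What the plan says.** SAP section 3.3.2.1 describes the endpoint as "defined as the sum of the insulin dose in U and U/kg from IMP and NIMP", so it is reported on two scales. Section 3.3.2.2 plans an "LS mean difference between treatments, as well as SE and 2-sided 95% CI", obtained "from MMRM with treatment, randomization stratum of HbA1c, randomization stratum of previous OADs, visits and treatment-by-visit interaction as fixed effects". That is the whole list of model terms. The strata are screening HbA1c split at 8% and type of oral antidiabetic treatment at screening (SAP section 1.1).

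Other continuous-endpoint models in the SAP carry a continuous baseline. The hypothetical-strategy MMRM for HbA1c and body weight (section 3.3.1.3) includes "appropriate baseline value and baseline-by-visit interaction as continuous covariate". The body weight ANCOVA (section 3.3.1.2) includes "randomization stratum of HbA1c and previous OAD and baseline body weight as covariates". Baseline characteristics in SAP Appendix 3 list "body weight in kg as quantitative variable", and HbA1c likewise.

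Protocol section 9.3.3.2 planned only descriptive statistics for total insulin dose. The SAP version history records that estimand attributes were added for this endpoint. Under that estimand, dose after treatment discontinuation is set to missing and handled by the MMRM under a missing-at-random assumption.

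**The concern.** The SAP turned a descriptive summary into a between-arm estimate with a standard error and confidence interval, but gave it a leaner model than the continuous endpoints around it. Reporting dose per kilogram suggests that the plan regards weight as relevant to dose. Weight is scheduled at screening and at Visit 2. HbA1c is scheduled at screening, so the model uses a two-level version of a value that exists in continuous form.

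Two things are at stake. The first is the width of the interval for the dose difference. The second is how plausible the missing-at-random assumption is for doses removed after discontinuation, since conditioning on baseline predictors of dose makes it easier to defend.

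**Working it through.** **What the plan's own figures give.** The documents state no standard deviation, power or interval width for insulin dose, so there is no dose figure to reproduce. The stated sample size supplies the number of evaluable participants. With margin 0.3, SD 1.05, true difference 0, one-sided 0.025 and 90% power:

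- n per arm = 2 × (1.960 + 1.282)² × (1.05/0.3)², which rounds up to 258. Dividing by 0.9 for dropout gives 287 per arm, 574 in total.
- The t-test version gives 259, then 288 per arm, 576 in total.

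Both agree with the planned 580 to within rounding up. Evaluable per arm: 290 × 0.9 = 261.

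**Effect of adding a continuous covariate.** Let ρ be the partial correlation between the covariate and Week 24 dose, given treatment and the two strata. Then

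width with covariate / width without = √(1 − ρ²).

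With 261 per arm, the 95% half-width in units of the residual SD is 1.96 × √(2/261) × √(1 − ρ²).

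| ρ (assumed) | Width ratio | Narrowing | Half-width (SD units) |
|---|---|---|---|
| 0 | 1.000 | 0% | 0.172 |
| 0.1 | 0.995 | 0.5% | 0.171 |
| 0.2 | 0.980 | 2.0% | 0.168 |
| 0.3 | 0.954 | 4.6% | 0.164 |
| 0.4 | 0.917 | 8.3% | 0.157 |
| 0.5 | 0.866 | 13.4% | 0.149 |

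If both covariates are added, ρ is read as their joint (multiple) partial correlation with dose.

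**Check by simulation.** A single-visit ANCOVA with 261 per arm and two binary strata was simulated with and without a continuous covariate. The ratios of standard errors were 1.001 at ρ = 0, 0.954 at 0.3 and 0.868 at 0.5. This agrees with the formula and shows that the price of a useless covariate is about 0.1%. The simulation was not a full MMRM.

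**Does the SAP have a reason to leave the covariates out?** The endpoint has, in general, no baseline value of its own, because Protocol section 5.2 excludes "Previous treatment with insulin (except for short-term treatment ≤ 14 days due to intercurrent illness" and similar exceptions) within the year before screening. Initiation of rescue medication has no baseline value either. Yet the SAP's logistic model for the binary endpoints in the same section 3.3.2.2 adjusts for continuous baseline HbA1c and further suitable baseline covariates. Absence of an own baseline therefore does not stop the SAP from adjusting elsewhere.

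**The case against.** The strongest defence is that the SAP follows a coherent rule for continuous endpoints: design factors plus the endpoint's own baseline where there is one. HbA1c, body weight, FPG, SMPG and C-peptide are all changes from baseline; insulin dose is not, and has no baseline. No other continuous model adds weight as a predictor of a different endpoint, and the body weight models also keep the HbA1c stratum. This stands as an explanation, so the omission is not a breach of the SAP's practice. The rescue model shows that it is not a necessity either.

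It is also fair that dose is titrated to fasting SMPG and not to weight, that iGlarLixi is capped at 40 dose steps while IDegAsp has no cap, and that U/kg already has weight as its divisor. Each may weaken the link between weight and dose, and all three stand as limits on the gain.

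A reader might go further and infer three things that the documents do not support:

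- *That the model adjusts for nothing at baseline.* It adjusts for two pre-randomization strata.
- *That the interval is certainly wider than the data allow.* That needs a partial correlation above zero, and the documents give none.
- *That a chance imbalance in weight biases the comparison.* Under randomization, leaving out a prognostic covariate does not bias the comparison as such.

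**Conclusion.** The point holds as a modest improvement in efficiency. If the partial correlation with dose in U is 0.2 to 0.5, the 95% interval narrows by about 2% to 13%. That range is an assumption; at 0.1 the gain is 0.5%, and at zero there is none. For U/kg the gain is less certain.

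Adjustment may also support the missing-at-random assumption, by an amount that cannot be put in figures from the documents. No formal decision depends on it: the endpoint is an other secondary one, carries no multiplicity-controlled test, and has an estimate and interval but no planned p-value. It is worth changing because the data are already collected and the downside is negligible.

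**What to change.** In SAP section 3.3.2.2, add baseline body weight and continuous baseline HbA1c to the total insulin dose MMRM, each with its by-visit interaction. Drop the HbA1c stratum, as the SAP already does wherever continuous HbA1c is in a model, and keep the previous-OAD stratum.

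State that starting dose is not a covariate. The investigator chooses it, within the protocol's limits, after the arm has been disclosed in an open-label trial (Protocol sections 6.1.4, 6.4 and 8.4.2.1), so it is a post-randomization variable. This is worth writing down because the same SAP section plans descriptive summaries of change from starting dose.

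The cost is one SAP sentence, with no new data, visits or participants.
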